13. DATA MANAGEMENT

13.1 Filling the CRFs and its handover

Data Management will identify and implement the most effective data acquisition and management strategy for the clinical trial protocol and deliver datasets which support the protocol objectives. Subject data will be entered into an e-CRFs in a validated data system.

13.2 Data entry and amendment

The data manager will prepare a Data Management Plan (DMP) to describe the procedures and processes of data collection and data coding (including data entry, data validation, data clarification process and database closure). For data coding (e.g., AEs, medical and surgical history, concomitant diseases, prior and concomitant medication), internationally recognized and accepted dictionaries will be used. The coding of the medical history, concomitant diseases and adverse events will be performed using MedDRA and the coding of concomitant medication by using WHO drug dictionary (WHODD). The clinical data will be reviewed for legibility, completeness, and logical consistency. Automated validation programs identify missing data, out-of-range data, and other data inconsistencies. Requests for data clarification will be forwarded to the investigative site for resolution. All plausibility checks will be defined in the Data Validation section of the DMP to be approved by the sponsor. Clinical data management will be performed in accordance with applicable CRO standards and data cleaning procedures with the objective of removing errors and inconsistencies in the data which would otherwise *Protocol N°: CVT-CV-002*

impact on the analysis and reporting objectives.

13.3 Locking the Database

At the completion of the data management activities and when the clinical data are clean, the

clinical database will be locked by the Data Manager and the clinical data released to the

statistician for the analysis. With database lock no further changes are allowed to the clinical

data.

14 STATISTICAL ANALYSIS

14.1 Datasets

Four populations will be defined:

1) Intention-To-Treat population (ITT): all randomized patients who will take at least one dose

of the study medication and with at least one available evaluation of efficacy after the baseline.

2) Per-protocol population (PP): all randomized patients from the ITT population without any

major protocol deviation; exact definition of major protocol deviations will be discussed by the

clinical team case by case during the blind review of the data.

3) Safety population: all randomized patients who will take at least one dose of the study

medication.

4) Pharmacokinetic population (PK): all randomized patients selected for the PK analysis (32)

total patients).

The primary efficacy endpoint will be analysed both in the ITT and in the PP populations; the

secondary efficacy variables will be analysed in the ITT population. The PK analysis will be

performed in the Pharmacokinetic population.

Analysis of safety variables will be performed in the safety population. In case of deviation

between as-randomised treatment and treatment actually received, the treatment actually

received will be used in the analysis of safety and PK variables (i.e. an as-treated analysis will

be performed).

14.2 Statistic Plan

All statistical analyses will be performed using Statistical Analysis Systems (SAS®) Software

(release 9.2) on a Windows 7 pro operating system.

Sample size

Protocol N°: CVT-CV-002

49

No formal sample size calculation has been calculated since there is no preliminary study to evaluate these endpoints at 24 hours after the infusion start.

In a previous study [14], there was a statistically significant decrease of the primary efficacy endpoint with istaroxime $0.5 \mu g/kg/min$ respect to placebo at 6 hours (twenty-nine patients in both groups). Since this study will investigate the primary efficacy endpoint at 24 hours and it is supposed that the profile at 24 hours should be similar to the one at 6 hours, it is expected that forty patients per group will be sufficient to evaluate a potential difference between istaroxime groups and placebo group on the primary efficacy endpoint at 24 hours.

Descriptive statistics

Descriptive statistics will be provided for each variable in summary tables by treatment group. Quantitative variables will be summarized by using n (sample size), mean, 95% confidence interval (CI) of the mean, median, standard deviation, minimum and maximum. Categorical variables will be summarized by using frequency count and percent distribution.

Principles of statistical analysis

For quantitative efficacy and safety variables, analysis within treatment groups will be presented. Mean changes from baseline and their 95% CIs will be calculated.

For all inferential analyses, p-value will be rounded to three decimal places. Statistical significance will be declared if the rounded p-value will be less than or equal to 0.05.

Subject's accountability

Disposition of patients, patient status and patients excluded from populations will be summarized by treatment group.

Description of the population-description of baseline characteristics

Descriptive statistics will be presented at baseline for demographic and baseline characteristics for the ITT population.

Primary efficacy endpoint

The primary efficacy endpoint (change from baseline in E/Ea ratio) will be analyzed using a linear mixed model for repeated measures including treatment, centre, timepoint, gender, baseline cTnT (normal <URL, abnormal ≥URL), atrial fibrillation (Yes/No) and treatment*timepoint interaction as fixed effects and baseline and baseline*timepoint interaction as covariates.

The primary comparison will be $0.5 \mu g/kg/min$ dose of istaroxime versus placebo at 24 hours. Highest dose of istaroxime (1.0 $\mu g/kg/min$) versus placebo will be tested as a secondary comparison.

Additional analyses separated by cohort will be implemented for sensitivity purpose.

Secondary efficacy endpoints

The following secondary endpoints:

- Change from baseline to 24 hours in the treatment period Day 1 (addressing the differences between the changes at 6 and 24 hours from baseline) of the following Echo-Doppler parameters:
 - o LV Ejection fraction (EF)
 - o LV end systolic and end diastolic volumes
 - o Stroke volume index (SVI)
 - o E, A and E/A ratio
- Change from baseline to 24 hours in the E/Ea ratio assessed by tissue Doppler (difference between the changes at 6 and 24 hours from baseline)
- Others Tissue Doppler parameters such as Sa, Da and Aa
- Changes in dyspnoea using VAS score will be analysed using a mixed model for repeated measures similar to the one used for the primary efficacy endpoint.

A global test considering multiple echocardiographic parameters at 6 and 24 hours will also be performed.

AUC on changes in dyspnea by VAS and changes in BNP will be analyzed using an ANCOVA model with treatment, centre, gender, baseline cTnT (normal <URL, abnormal ≥URL) and atrial fibrillation (Yes/No) as fixed effects and baseline dyspnea as covariate.

Number and proportion of patients with:

- hospital readmissions or emergency visits for cardiovascular reasons within Day 30
- episodes of worsening HF defined by the need to increase the dose or reinitiate i.v. therapy with diuretics and/ or other inotropic agents during the hospitalization

will be summarized by treatment groups using descriptive statistics.

Length of hospitalization will be summarized by treatment group using descriptive statistics.

Safety endpoints

The number and the percentage of patients experiencing adverse events, adverse drug reactions, serious adverse events and adverse events leading to study withdrawal will be summarized by treatment group. Adverse events will also be summarized by treatment group by means of System Organ Class and Preferred Term using the MedDRA dictionary.

Vital signs (including body temperature and dyspnoea), 12-lead ECG parameters, incidence of clinically or hemodynamically significant episodes of supraventricular or ventricular arrhythmias, laboratory parameters, renal function, cTNT, increase of cTNT and mortality will be summarized by treatment group using descriptive statistics.

Interim Analysis

A safety interim analysis on cTNT changes is planned after the completion of Cohort 1.

Protocol N°: CVT-CV-002

PK analysis of istaroxime and its metabolites

PK parameters C_{max} , AUC_{0-t} , $AUC_{0-\infty}$ (if feasible) and A_e for istaroxime and its metabolites will be analysed using analysis of variance (ANOVA). The data will be dose-normalised and transformed prior to analysis using a neperian logarithmic transformation.

The statistical analysis will take into account gender, dose, centre, baseline cTnT (normal <URL, abnormal ≥URL) as fixed factors. The statistical method for testing linearity is based upon the 90% confidence interval for the ratio of the population geometric means (Dose1/Dose2), for the parameters under consideration. This method is equivalent to the corresponding two one-sided test procedure with the null hypothesis of no linearity at the 5% significance level.

Acceptance criterion for linearity will be a 90% confidence interval of the ratio of geometric means within the range 75.00 - 133.33%.

t_{max} will be analyzed using a non-parametric model providing an estimate and 90% CI to the median difference of dose pairs.

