3. STUDY DESIGN

This is a phase II, multicenter, randomized, double-blind, placebo-controlled, parallel group study.

96 Chinese patients and 24 Italian patients will be randomly assigned to one of two doses of istaroxime or placebo in a 2:1 ratio within two sequential cohorts of 60 patients each.

This 31-day study includes a screening period (Days -1), a treatment period (Day 1), a post-treatment period (Days 2-4), and a follow-up period (which includes one patient visit on Day 30).

When a patient is considered fully eligible (i.e. s/he fulfills all the inclusion criteria and does not meet any exclusion criteria as stipulated), the patient will be randomized. Treatment details are presented below:

Cohort I: 0.5 µg/kg/min istaroxime or placebo (40 patients randomized to istaroxime 0.5 µg/kg/min group and 20 patients randomized to placebo group).

Istaroxime 0.5 μ g/kg/min (30 μ g/kg/h) continuous i.v. infusion for 24 hours **not exceeding 72** mg per 24 hours for patients with body weight > 100 kg

Cohort II: 1.0 μ g/kg/min istaroxime or placebo (40 patients randomized to istaroxime 1.0 μ g/kg/min group and 20 patients randomized to placebo group).

Istaroxime 1.0 μ g/kg/min (60 μ g/kg/h) continuous i.v. infusion for 24 hours **not exceeding 144** mg per 24 hours for patients with body weight > 100 kg

Escalation to the next dose (second cohort) will occur after completion of the first cohort and determined by the evaluation of the safety data performed by the Data Safety Monitoring Board.

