12. PHARMACOKINETIC ASSESSMENT

Plasma concentrations of istaroxime and its metabolites PST2915, PST2922, and PST3093 will

be measured by liquid chromatography coupled to mass spectrometry (LC/MS/MS). When applicable, E and Z isomers will be measured separately.

In a subset of patients, a blood sample will be collected during the study period. In addition, a full PK profile will be established in a subset of Italian patients and in a subset of Chinese patients (to have 16 patients with istaroxime 0.5 μ g/kg/min and 8 patients with istaroxime 1.0 μ g/kg/min 24 total patients).

Blood will be sampled at the following time-points: 0 hour (pre-dose); 0.5, 3, 6, 12, and 24 hours after infusion start; 0.25, 0.5, 1, 4, 12, 24 hours after infusion end.

In the same subset of patients, concentrations of istaroxime and its metabolites will be measured by LC/MS/MS in urine collected from pre-dose to 48 hours after infusion end (3 collections will be scheduled: the first from pre-dose to 24 hours after investigational product infusion start, the second at 48 hours after infusion start, and the third at 72 hours after infusion start).

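### Fixed centre effects in the PK dose-linearity ANOVA can remove much, or in the extreme all, of the information on the dose ratio; country should replace centre

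*Protocol*

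**What the plan says.** Protocol section 14.2 (PK analysis) applies an ANOVA to log-transformed, dose-normalised Cmax, AUC and A_e: "The statistical analysis will take into account gender, dose, centre, baseline cTnT" class, as fixed factors. The decision rule is: "Acceptance criterion for linearity will be a 90% confidence interval of the ratio of geometric means within the range 75.00 - 133.33"%. The protocol adds: "This method is equivalent to the corresponding two one-sided test procedure with the null hypothesis of no linearity at the 5% significance level".

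Section 12 sets the size of the full-profile subset: "to have 16 patients with istaroxime 0.5" µg/kg/min "and 8 patients with istaroxime 1.0" µg/kg/min, 24 in total. Section 14.1 gives a different total for the PK population: "all randomized patients selected for the PK analysis (32" in total), with no split by dose.

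Section 3 assigns patients "within two sequential cohorts of 60 patients each", with 0.5 µg/kg/min in the first cohort and 1.0 in the second. Randomisation is 2:1 istaroxime to placebo within a cohort and is stratified by centre and atrial fibrillation (section 5.2). It does not allocate patients between the two doses.

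The SAP lists the PK parameters (section 3.2) but specifies no linearity model. Section 5 has no PK analysis set, section 7.9 (other planned analyses) is empty, and the only PK-specific code in section 9.0 is a Wilcoxon test for Tmax. Section 1.1, which lists changes from the protocol, does not mention PK.

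**The concern.** A fixed centre term means that the dose ratio is estimated only by comparing patients within the same centre. In a trial that randomises to dose within centre, this costs little. Here dose changes between cohorts that run one after the other, and the PK subset is small. A centre may therefore have PK patients from one cohort only. Such patients still yield concentrations but carry no direct information on dose proportionality, and each further centre also uses a degree of freedom.

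Linearity is accepted only if the whole 90% interval lies inside the limits, so a wider interval means more failures to show linearity when it is true. At stake is whether the trial can answer its own question about dose proportionality. The primary efficacy comparison is not affected.

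**Working it through.** **The plan's own figures.** A 90% interval corresponds to two one-sided tests at (1 − 0.90)/2 = 0.05, as stated. The limits are symmetric on the log scale: 1/0.75 = 1.3333 and ln(1.3333) = 0.2877. Section 12 adds up: 16 + 8 = 24. No power, CV or number of centres is given for the PK analysis.

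**Information within centres.** If centre k has a_k patients at the lower dose and b_k at the higher, then in a model with dose and centre

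SE(log ratio) = σ / √[Σ a_k b_k / (a_k + b_k)], with σ = √ln(1 + CV²).

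A single-dose centre has a_k b_k = 0 and adds nothing. Examples:
- No centre term: 16 × 8/24 = 5.333, so SE = 0.433σ.
- Four centres of 4 + 2: 4 × 8/6 = 5.333, so SE = 0.433σ. Only degrees of freedom are lost.
- Centres of 4 + 2, 4 + 2, 8 + 0 and 0 + 4: 2 × 8/6 = 2.667, so SE = 0.612σ. Half the patients drop out.
- No centre with both doses: the sum is 0 and the ratio is not estimable.

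As a check, fitting simulated data in the third layout with and without the 12 patients in single-dose centres gave the same dose estimate (−1.0527 both times).

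At an assumed CV of 25%, σ = √ln(1.0625) = 0.246. The typical half-width of the 90% interval is 1.717 × 0.433 × 0.246 = 0.18 without centre (22 df) and 1.729 × 0.612 × 0.246 = 0.26 in the third layout (19 df). The limit is 0.288.

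**Power for given layouts** (true ratio 1, 16 v 8 patients; assumed 25% in the minority gender and 80% with abnormal cTnT):

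| Model and layout | CV 20% | CV 25% | CV 30% |
|---|---|---|---|
| Dose only | 89% | 67% | 42% |
| Dose + gender | 88% | 65% | 40% |
| Dose + gender + cTnT | 86% | 61% | 36% |
| Planned model, 4 centres, all 2:1 | 85% | 60% | 35% |
| Planned model, 8 centres, all 2:1 | 83% | 57% | 32% |
| Planned model, 14 of 24 in mixed centres (4 centres) | 60% | 29% | 11% |
| Planned model, 12 of 24 in mixed centres (4 centres) | 42% | 15% | 4% |
| Planned model, 8 of 24 in mixed centres (6 centres) | 16% | 3% | 1% |

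At CV 25%, adding cTnT to dose and gender costs 65 − 61 = 4 points. With both doses in every centre, adding centre costs a further 61 − 60 = 1 point (4 centres) or 61 − 57 = 4 points (8 centres).

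**Random spread over centres** (simulated, CV 25%, 25% in the minority cTnT class). With 4, 8 and 12 centres, on average about 1.7, 6.4 and 10 of the 24 patients sit in single-dose centres. Power of the planned model is about 46%, 32% and 19%. Dose + gender + country gives about 59% to 60%. A more favourable approximation gives 58%, 42% and 28% for the planned model. It evaluates power at the median SE of a dose-and-centre model and charges gender and cTnT only one degree of freedom each.

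**Dropping geography altogether.** Assume a 20% exposure difference between countries, CV 20%, a true ratio of 133%, and a country mix that differs by dose in the direction that masks non-linearity. Dose + gender then falsely accepts linearity in about 10% to 12% of trials with 12 of 16 v 4 of 8 Italian patients, and in about 31% to 35% with 14 of 16 v 2 of 8. Adding country brings this back to about 5%.

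**The case against.** The strongest reply is that the size of the loss rests on inputs the documents do not give. No section says that any centre has PK patients at one dose only, and with both doses in every centre the loss is modest. That stands: a large loss is possible, not established. Random spread is also only one assumption. Protocol sections 2 and 6.3 place all Italian patients in the PK study, while sections 7 and 12 speak of a subset, so PK patients may be concentrated by country. The total is unsettled too: with 32 patients, dose-only power at CV 25% would be 85% to 89%, assuming a 16/16 or 21/11 split.

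The second reply is that centre protects validity. This also stands in part. A reader might infer that centre can be dropped at no cost because one laboratory assays all samples. The documents do not support that. Infusion preparation, pump rates, sampling and 24-hour urine collection happen at the centres, and the two doses are not randomised against each other. Some geographic adjustment is needed.

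A reader might also infer that baseline troponin shares the blame. It is a small contributor, and it is not plainly unrelated to exposure: section 6.2 ties its interpretation to renal function, and A_e measures urinary excretion.

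Finally, this is a secondary analysis with no power target, the planned model errs on the conservative side, and the estimated ratio would be reported in any case. That limits the weight of the point but does not remove it.

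**Conclusion.** The point holds as a cheap improvement to a secondary analysis. That single-dose centres add essentially nothing to the dose ratio is algebra and needs no assumption. The size is conditional. Power falls about 4 to 10 points below dose-only if every centre has both doses at 2:1. At CV 25% with random spread, it falls from about 60% under the country model to about half that at 8 centres (32%) and about a third at 12 (19%). The ratio is not estimable if no centre has both doses.

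It would go too far to say that the planned analysis will lose half its power, since the documents fix neither the layout nor the CV. Nor would the change rescue the test if variability is high: at CV 30% even the dose-only model has 42% power. The figures assume 16 v 8 patients, and the conflict between 24 and 32 must be settled before any of them is relied on.

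**What to change.** In Protocol section 14.2, and in a new PK section of the SAP, specify ln(dose-normalised parameter) = dose + gender + country (Italy/China). Keep the 90% interval and the 75.00–133.33% limits. Country should be required, not optional, for the reason shown by the false-acceptance figures. Keep the planned model with centre and baseline cTnT as a sensitivity analysis.

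Reconcile the PK total (24 v 32) and whether all or some Italian patients take part, and define the PK set in the SAP. The country term follows the same algebra as centre, so the plan should also state that PK patients at both doses are to be sampled within each country.

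The model change costs one line of analysis wording and no new data. Its downside is that centre differences within a country are left unadjusted in the main PK analysis; the sensitivity analysis addresses them as far as the layout allows.

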15. QUALITY CONTROL AND QUALITY ASSURANCE

During the trial, monitor will be appointed by Sponsor to visit the study centers regularly, in order to ensure rigorous performance of all contents in the protocol and accuracy of study materials.

Investigators must attend unified training to unify the record manner and the judgment standard.

- the clinical trial process should be strictly conducted in a blind state.
- Investigators should fill in the CRF accurately, detailed, and seriously according to the requirements, to insure that contents of the CRF are true and credible;
- Judgment standard of laboratory examination abnormality should be subject to the normal range of the centers;
- •All observation results and findings of the trial should be verified to ensure the reliability of the data and that each conclusion comes from source data. Corresponding data management should be taken during the trial and data processing period;
- For possible drop-out, active measures should be taken to keep the dropout rate within 20%.

15.1 Drug Accountability

The Investigator must ensure the maintenance of accurate records of the amounts and dates investigational products were received from the Sponsor, dispensed and unused supplies returned or destroyed. All clinical supplies must be accounted for at the termination of the study and a written explanation provided for discrepancies. All unused supplies must be returned promptly to the Sponsor or destroyed properly at the study site; written authorization from the Sponsor must be obtained prior to destruction. The Investigator will maintain a record of the amount and dates when unused supplies were returned to the Sponsor or destroyed locally. When the above tasks are delegated to a Pharmacist, the latter is under the supervision of the Investigator, who remains ultimately responsible for the maintenance of accurate drug dispensing records.

16. MONITORING AND STUDY COMMITTEES

16.1 Monitoring

CVie Therapeutics Company Limited, Hong Kong, is the study Sponsor. CVie Therapeutics will delegate CROs (CROS NT, Verona and CRONOS Srl, Ravenna) for the operational aspects of the study (set up, e-CRF and data management) and for monitoring of the Italian centers. Local operational representatives will be determined in each participating country before the launch of the study.

At mutually convenient times during the study, the Investigator will allow CVie Therapeutics or its representative to review all completed e-CRFs and related source documentation, i.e. patients' office, hospital, clinic and laboratory records. At timely intervals, and at the closing of the study, all investigational products will be accounted for, and dispensing records will be made available to CVie Therapeutics or its representative.

In case CRFs require support information, CVie Therapeutics may request copies of patient records or other source documents from the Investigator. All necessary steps will then be taken to protect patient identity. Adherence to local and national laws governing protection of patient identity will be ensured.

